8.7 Study Monitoring

As per ICH-GCP 5.18 and FDA 21 CFR 312.50 clinical protocols are required to be adequately monitored by the Sponsor. This study monitoring will be conducted according to the “NIAID Intramural Clinical Monitoring Guidelines.” The Sponsor will monitor all aspects of the study, with respect to current GCP, for compliance with applicable government regulations. Prior to the start of the study, the investigator will be informed of the frequency of monitoring visits and will be given reasonable notifications prior to each visit. The objectives of a monitoring visit will be to verify the prompt and accurate recording of all monitored data points, and prompt reporting of SAEs; to check the availability of signed informed consent forms and documentation of the informed consent process for each monitored subject; to compare CRIMSON reports and line listings with source data for completeness and accuracy; and to help ensure investigators are in compliance with the protocol. The monitors also will inspect the clinical site regulatory files to ensure that regulatory requirements (Office for Human Research Protections-OHRP, FDA) and applicable guidelines (ICH-GCP) are being followed. During the monitoring visit, the investigator (and/or designee) and other study personnel should be available to discuss the study. Study documents must be available for review throughout the course of the study. The Sponsor will retain original copies of the Form FDA 1572 and copies of other study documents as deemed necessary.

The investigator (and/or designee) will make study documents (e.g., consent forms, CRIMSON and pertinent hospital or clinical records) readily available for inspection by the local IRB, FDA, the site monitors, and the NIAID staff for confirmation of the study data.

A specific protocol monitoring plan will be discussed with the PI and study staff prior to enrollment. The plan will outline the frequency of monitoring visits based on such factors as study enrollment, data collection status and regulatory obligations.

9 STATISTICAL CONSIDERATIONS

9.1 General Design

The major objectives of this Phase 1 ZIKV trial are to identify a suitable ZIKV CHIM strain to aid in the selection of vaccine candidates and to characterize the clinical and virologic characteristics of ZIKV infection.

9.2 Statistical Methods

This study, like other Phase 1 studies, is exploratory rather than confirmatory. As such, the primary analyses will assess frequencies of adverse events and describe patterns of challenge virus replication and immune response within individuals at multiple timepoints (e.g. pre vs post challenge), and within and between groups (challenge virus vs. placebo).

Continuous outcomes (e.g. peak titer of virus shed, antibody titers over time) will be presented with the use of summary statistics such as means, medians, quartiles, ranges, etc. as appropriate, with data displayed in both tables and figures. Student’s T-tests and linear regression will be used to assess differences in continuous outcomes between subjects in each study arm. Correlations between 2 continuous outcomes will be evaluated with the use of Pearson or Spearman correlation coefficients and graphed as scatterplots.

Proportions of subjects with dichotomous outcomes of interest (e.g. presence or absence of: specific AEs, viral shedding, seropositivity, four-fold rise in antibody response, etc.) observed in each group will be summarized in tables and figures. Differences in proportions between groups will be compared with χ^2 tests, Fisher's exact tests, and logistic regression as appropriate. Outcomes will be summarized by severity and/or category where applicable (e.g. immediate, systemic, local AE).

The study is powered to detect a difference in the occurrence of virus in blood, urine, cervico-vaginal secretions, or saliva following administration of one of 2 ZIKV at different doses, compared with placebo recipients. A sample size of 10 ZIKV recipients and 4 placebo recipients will be able to detect a statistically significant difference ($\alpha = 0.05$) in recovery of infectious ZIKV from the blood between the ZIKV and placebo groups at a power of 0.99 with $\geq 80\%$ of ZIKV-inoculated subjects having detectable ZIKV viremia and 0 placebo recipients having detectable ZIKV in blood and body secretions. The detection of ZIKV by RT-PCR and by virus culture from blood, urine, cervico-vaginal fluids, semen and saliva in recipients of each ZIKV strain will be compared to placebo recipients. In addition, the magnitude and duration of ZIKV presence in blood, urine, cervico-vaginal secretions, semen and saliva will be compared to one another at each dosing level. The effect of dose escalation on the presence of virus in blood, urine, saliva, cervico-vaginal secretions and semen will also be evaluated. Multiple comparisons analysis will be used to compare the magnitude and duration of virus presence at each dose level of each candidate ZIKV and placebo recipients.

Measuring the transmissibility of ZIKV-SJRP and ZIKV-Nicaragua from infected volunteers to mosquitoes is an exploratory endpoint. Following feeding on volunteers, mosquitoes will be returned to the NIH for analysis (Section 6.7). The heads and thoraces of the mosquitoes will be examined for ZIKV antigen. If antigen is detected in the head of the mosquitoes, it will be assumed that the virus escaped the mid-gut barrier and is present in the salivary glands.

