174 of 1,230 (14%) semen samples tested from those men [30]. Of the 174 semen samples that were positive for ZIKV by RT-PCR, infectious virus (as determined by recovery in tissue culture) was found in only 4% of the samples. In addition, infectious virus was found only in samples collected within 30 days of symptom onset [30]. Only 6.5% of the men tested shed infectious ZIKV in semen. In the Mead study, infectious virus was detected in only 3 of 19 semen samples that were obtained within 30 days of illness; infectious virus was not detected in any of the 59 samples that were detected after day 30 of illness onset (Figure 1). The 3 samples that were positive for infectious virus had titers $\geq 7 \log_{10}$ RNA copies/mL of semen and were the only samples that had titers $\geq 7 \log_{10}$ RNA copies/mL of semen [30]. A second study collected 700 semen samples from 97 confirmed ZIKV-infected men [35]. Thirty-two of the 97 men (33%) had at least one semen specimen

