positive for ZIKV by RT-PCR. Infectious virus was isolated from RT-PCR-positive semen samples from 8/32 men (25%) or 8/97 total (8.2%). Few subjects had ZIKV shedding detected in saliva (15/147; 10.2%) and only 1 woman had ZIKV shedding detected in cervico-vaginal secretions (1/50; 2%). Isolation of infectious virus was not performed for saliva or cervico-vaginal secretion specimens. Aside from the Paz-Bailey study above, few studies have evaluated shedding of ZIKV in cervico-vaginal secretions in a longitudinal manner [36-38] and of those studies even fewer have evaluated for infectious virus [39]. Viral RNA was generally detected in vaginal secretions or brush samples by RT-PCR for ~ 2 weeks post-symptom onset [29, 36-38]. There are 2 reports of longer vaginal shedding of ZIKV. The first reported ZIKV vaginal shedding in 5 women, 4 of whom were pregnant women [40]. One pregnant woman shed ZIKV vaginally for 180 days. Testing for infectious virus was not done. A second case reported vaginal shedding at 31 days post-symptom onset [41]. The titer was very low (200 genomic copies/mL) and testing for infectious virus was not done. It is also not known for how long ZIKV can be sexually transmitted, but all cases of sexual transmission reported in the literature thus far have occurred within 3 weeks of return from an endemic area with all but one of those cases occurring within 2 weeks [24, 26-28, 42]. The primary method of viral detection in these studies was by RT-PCR. When samples were evaluated for infectious virus by tissue culture, infectious virus was found in the minority of samples as noted above. In the Medina study, all but one semen sample containing infectious ZIKV were obtained within 15 days of symptom onset. The mean titer by polymerase chain reaction (PCR) \pm standard deviation (SD) in those 8 semen samples that contained infectious virus was $1.8 \times 10^8 \pm 2.5 \times 10^8$ genome copy equivalents (GCE) per mL. The mean titer \pm SD for serum samples that contained infectious virus was $4.8 \times 10^7 \pm 1.1 \times 10^7$ GCE/mL. Medina *et al.* concluded that specimens with a titer $>1.4 \times 10^6$ GCE/mL be considered infectious [35]. **These data suggest that the shedding of infectious ZIKV in semen may occur much less frequently and for a shorter duration than presumed by RT-PCR testing** and are

[figure not shown]

Figure 1: Estimated Viral RNA Load and Culture Results in Semen from 184 Men (Mead et, al 2018)

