The primary objective of this study is to identify and characterize a suitable ZIKV strain for use in future ZIKV controlled human infection models (CHIM). The use of a ZIKV CHIM will be critical for evaluation and down-selection of candidate ZIKV vaccines. Because ZIKV congenital syndrome can occur with asymptomatic infection and infection during any trimester, it is likely that a ZIKV vaccine will need to induce protection against ZIKV viremia to prevent congenital infection. Prevention of symptoms in the mother may not be sufficient to prevent congenital Zika syndrome. The ability of a vaccine to prevent ZIKV viremia (sterilizing immunity) can best be evaluated in a CHIM, prior to Phase 2 or Phase 3 studies. In addition, the ZIKV epidemic has waned over the past 2 years and modelling exercises predict that, in the future, outbreaks may occur only once every 10 years [44]. For this reason, it is not likely that there is sufficient predictable ZIKV transmission for a Phase 3 efficacy study to be performed and the efficacy of candidate ZIKV vaccines may only be able to be determined by CHIM studies. As stated above, the value of a ZIKV CHIM was affirmed at a recent WHO/NIH consultation on immune correlates of protection for ZIKV [43]. Because of the current lack of ZIKV transmission and the important role that a ZIKV CHIM can play in the pathway to licensure of a ZIKV vaccine, the consultation concluded that a ZIKV CHIM was ethically justified at this time should the studies sufficiently mitigate the risk of CZS and the risk of third-party transmission [43]. A ZIKV CHIM could also be critical to the development and licensure of diagnostics and therapeutics for ZIKV.

A secondary objective of the protocol is to further define the clinical presentation, viral replication, and sites and duration of ZIKV shedding following infection in healthy adult women and men. This study will contribute to the body of knowledge related to ZIKV infection and transmission. Although the data from natural ZIKV cases suggest that the risk of sexual transmission from men to women does not appear to be high, there are gaps in that knowledge.

We will enroll men to evaluate the shedding of infectious ZIKV in semen to advance knowledge of the risk of sexual transmission from men to women.

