3.1.2 Study Design

This study will include 4 cohorts of 14 ZIKV and DENV-naïve female and male subjects, 18 - 40 years of age (total: up to 56 subjects). Within each cohort, 10 subjects will receive ZIKV and 4 subjects will receive a placebo on Study Day 0. Cohorts 1 and 2 (Dose = 10^2 PFU) will be enrolled first and will enroll only women. Cohorts 3 and 4 (Dose = 10^2 PFU) will enroll men.

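### Semen shedding should be estimated with an exact confidence interval; the planned comparison with placebo men says almost nothing about infectious virus at the rates the protocol cites

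*Combined protocol and SAP*

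**What the plan says.** Section 1.1 gives a purpose for the male cohorts: "We will enroll men to evaluate the shedding of infectious ZIKV in semen to advance knowledge of the risk of sexual transmission". Section 4 likewise says men are enrolled to quantify infectious shedding in semen. Section 2.1 lists frequency, magnitude and duration of virus in semen among the suitability measures, and section 2.2 lists quantity and duration in semen.

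On size, section 3.1.2 says "Within each cohort, 10 subjects will receive ZIKV and 4 subjects will receive a placebo on Study Day 0" and "Cohorts 3 and 4 (Dose = 10^2 PFU) will enroll men". There is one male cohort per strain, so 10 virus recipients per strain and 8 placebo men in all.

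On analysis, section 9.2 says virus detection by RT-PCR and culture, with "semen and saliva in recipients of each ZIKV strain will be compared to placebo recipients". It does not say whether the comparator is the 4 placebo men of the same cohort or a pooled group. Proportions are to be compared by chi-square tests, Fisher's "exact tests, and logistic regression as appropriate". Sidedness is not stated. The power statement names blood, urine, cervico-vaginal secretions and saliva, but not semen, and its only assumed rate is at least 80% in blood. Section 9.2 also calls the study exploratory and plans to summarise shedding proportions by group. Section 9 plans no confidence interval.

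**The concern.** A ZIKV-naive placebo recipient has no virus to shed. Section 1.3.2.3 reports none recovered from any placebo specimen in cohort 1. Comparing inoculated men with placebo men therefore tests whether the shedding rate differs from a value known to be zero. The useful question is how large the rate is, which is a one-sample estimate, and its uncertainty is not in the plan.

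Section 4 says the semen data will help assess the risk of male-to-female transmission. A result such as no shedders in 10 men, with no significant difference from placebo, could be read as reassurance although it is compatible with rates well above those already reported. An interval would show this; a p-value would not.

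**Working it through.** **Inputs.** 10 virus and 4 placebo men per strain, 8 placebo men in total (3.1.2); alpha 0.05 (9.2); infectious virus in semen in 6.5% of men in one cited study and 8/97 = 8.2% in another, and RT-PCR positivity in 60/184 = 33% (1.1). Placebo shedding is taken as zero.

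**The plan's own figure.** For blood, section 9.2 says 10 against 4 "will be able to detect a statistically significant difference" with power 0.99 at 80% against 0%. Normal approximation: pooled proportion 8/14 = 0.571; null SE = √(0.571 × 0.429 × (1/10 + 1/4)) = 0.293; alternative SE = √(0.8 × 0.2/10) = 0.126. One-sided: (0.8 − 1.645 × 0.293)/0.126 ≈ 2.52, power 0.994. Two-sided power is 0.963. The 0.99 thus reproduces one-sided, and no such figure is given for semen.

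**Positives needed, with none on placebo.** Fisher, 8/10 against 0/4: C(10,8)/C(14,8) = 45/3003 = 0.015. For 7/10: 120/3432 = 0.035 one-sided, 0.070 two-sided. Uncorrected chi-square for 6/10: 0.36/(0.429 × 0.571 × 0.35) = 4.2, p = 0.040. The other thresholds follow the same way.

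**Power** is P(X ≥ k) for X binomial(10, p):

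| Placebo men | Test | k needed | p = 6.5% | p = 8.2% | p = 33% |
|---|---|---|---|---|---|
| 4 | Fisher, two-sided | 8 | <0.001% | <0.001% | 0.3% |
| 4 | Fisher, one-sided | 7 | <0.001% | <0.001% | 1.9% |
| 4 | chi-square, two-sided | 6 | 0.001% | 0.005% | 7.3% |
| 4 | chi-square, one-sided | 5 | 0.02% | 0.07% | 20.6% |
| 8 pooled | Fisher, either | 5 | 0.02% | 0.07% | 20.6% |
| 8 pooled | chi-square, two-sided | 4 | 0.3% | 0.6% | 43% |
| 8 pooled | chi-square, one-sided | 3 | 2.3% | 4.3% | 69% |

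Logistic regression is also listed. With no positive placebo man the estimated odds ratio is infinite, so a Wald test is unusable. A likelihood-ratio test at 4/10 against 0/4 gives G² = 2[4 ln(0.4/0.286) + 6 ln(0.6/0.714) + 4 ln(1/0.714)] = 3.29, p = 0.070 two-sided or 0.035 one-sided. Its one-sided power is 0.3-0.6% at 6.5-8.2%. Against 8 pooled men it needs 3/10, as the one-sided chi-square does, so the 2-4% ceiling for infectious virus stands.

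**Chance of seeing no shedder.** (1 − p)^10 = 0.511 at 6.5% and 0.425 at 8.2%. For 20 men: 0.261 and 0.181.

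**What a zero would show.** The two-sided exact 95% upper bound for 0/n is 1 − 0.025^(1/n): 30.8% for n = 10 and 16.8% for n = 20. To fall below 8.2%, n must exceed ln(0.025)/ln(0.918) = 43.1, so 44 men. Only 20 receive virus.

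**The case against.** **The plan already describes shedding.** Section 9.2 calls the study exploratory and summarises shedding proportions by group, and Tables 5 and 7 report other fluids as simple frequencies with titre, onset and duration. This stands. A reader might infer that the placebo test replaces estimation of semen shedding; the documents do not support that. What is missing is the interval.

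**The comparison is not doomed for RT-PCR.** A reader might infer that the test cannot reach significance and will almost certainly report no difference from placebo. For RT-PCR that is too strong. The comparator is not fixed at 4 men, chi-square is allowed, and pooled power at 33% runs from about 21% to 69%.

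**Natural-infection rates may not transfer.** Section 1.1 cites RT-PCR positivity of 10.2% in saliva and 2% in cervico-vaginal secretions after natural infection. After challenge, Tables 5 and 7 show 70% and 100% in saliva, 50% and 80% in cervico-vaginal secretions, and 80% in urine for both strains (10 and 5 women). If semen RT-PCR behaved similarly, Fisher power against 4 men (two- to one-sided) would be 5-17% at 50%, 38-65% at 70% and 68-88% at 80%. Culture results after challenge also vary: 30% and 100% in saliva, but 10% and 0% in cervico-vaginal secretions. This stands as a limit on every power figure here.

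**The 6.5% figure is hard to trace.** Section 1.1 states "Only 6.5% of the men tested shed infectious ZIKV in semen", yet describes 3 infectious samples among 19 early and 59 later ones; 6.5% of 184 would be about 12 men. The 8.2% has a clear numerator and denominator, and the conclusion is the same with it alone.

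**No decision rests on this p-value.** Strain suitability depends on viremia by culture, and barrier contraception for men through Day 90 is fixed. The Precis also gives replication kinetics and mosquito transmissibility as purposes of the male cohorts. All true. The risk is misreading of a safety-relevant result, not a wrong trial action.

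**Conclusion.** The point holds for infectious virus, the measure sections 1.1 and 4 single out. At 6.5-8.2%, the placebo comparison has below 0.1% power by Fisher or chi-square against a cohort's 4 men and at most about 2-4% under the most favourable variant. For RT-PCR the comparison is weak at 33% with 4 placebo men (0.3-21% by Fisher or uncorrected chi-square) but not hopeless with pooling or a higher rate. A cohort with no infectious shedder is about as likely as not (43-51%), and neither 0/10 (upper bound 31%) nor 0/20 (17%) could exclude the natural-infection rate. The power figures and the chance of a zero assume that natural-infection rates apply after challenge; the upper bounds do not. Nor does the mismatch between the comparison and the question: placebo men cannot inform the shedding rate in inoculated men. This is worth changing because the better analysis costs nothing in data; it is not a defect that undermines the trial.

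**What to change.** In section 9.2, replace the semen-versus-placebo comparison as the main semen analysis with two proportions: ZIKV-inoculated men with any culture-positive semen sample, and with any RT-PCR-positive semen sample. Give each with a two-sided exact (Clopper-Pearson) 95% confidence interval, per strain and for cohorts 3 and 4 combined. If the placebo comparison is kept, name the comparator (own cohort or pooled male placebo) and label it descriptive. Add one sentence saying that zero shedders among 10 or 20 men cannot show a rate below that reported in natural infection.

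Cost: a wording change to the analysis section, with no extra subjects, samples or assays. The intervals will be wide and the reported conclusion more cautious.
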